## **(2) Adequacy of Protection from Risks**

(a) Recruitment and Informed Consent: Subjects will be recruited voluntarily. At each recruiting site, we will enroll 3-4 subjects per month, over 30 months, for a total of up to 185 subjects. All persons with COPD who meet our inclusion criteria will be eligible to participate in the proposed research. Our recruitment method will consist of mailings with the options to express interest by calling study staff or returning a postcard. All subjects who do not respond to the mailing will receive a telephone call from study staff. Interested participants will be scheduled for a screening visit. Study staff will explain the nature, scope, and possible consequences of the study in a form understandable to participants and answer all their questions. Subjects are under no obligation to participate. Written informed consent will be obtained at the time of screening by study staff.

### **(b) Protection Against Risks.**

Subjects will be eligible to participate in the study only if they have medical clearance from their healthcare provider to participate in an exercise program. We estimate the total time of testing to be approximately 3 hours per study visit, with additional time at VABoston site of up to 60 minutes at the baseline and 12-month visits that include DXA scans. We will not perform bioimpedance measurements in any subject with a pacemaker or defibrillator to minimize any potential risks. The study PI or covering physician are on site during testing and available for

questions. Staff performing the spirometry and 6MWTs will be trained in Basic Life Support. Emergency treatments including nebulizer therapy, an automated external defibrillator, and a code cart will be available. During the pulmonary function tests and 6MWTs, subjects can rest if short of breath and will be allowed to use supplemental oxygen if usually prescribed. Safety for administration of albuterol for the post-bronchodilator spirometry will be assessed with a checklist of symptoms. For the walk test, subjects will be instructed to bring their medications to the visit and will be allowed to take their usually prescribed bronchodilators if needed after performing the walk test. We exclude subjects at higher than usual risk of adverse effects from a walking exercise program. For example, subjects will be screened for active cardiovascular disease by history and for exercise-induced hypoxemia during the walk test. If hypoxemia, oxygen saturation <85%, is observed during the 6MWT, subjects will be temporarily excluded from further study participation and their primary provider contacted for further care. These subjects can be reassessed for eligibility at a later date when clinically stable. Hypoxemia and dyspnea predict balance impairment and falls in COPD; both are assessed right before the 6MWT is performed. Also, if the subject is unsteady on his feet during the short walk to assess pedometer accuracy and is obviously a fall risk, the 6MWT will not be performed.

Venipuncture will be performed by staff trained in phlebotomy. Subjects do not have to answer any questions on questionnaires with which they are uncomfortable. Inadvertent disclosure of medical history information is guarded against by maintaining completed questionnaires in a locked filing system. We will evaluate for depression with the Beck Depression Inventory. Patients with a Beck total score  $\geq 14$  will, with the patient's permission, have their primary providers informed of the results, with the suggestion that they might consider referral for evaluation and/or treatment. Additionally, the PI will be notified if participants report suicidal thoughts on question 9 of the Beck's, and the PI will evaluate the patient for need for referral to the ER for further evaluation and treatment. The clinical diagnosis of depression or anxiety will need to come from the participants' mental health or primary care providers, we are not diagnosing it in the research study.

If subject has previously undergone a DXA scan at the VA Boston Osteoporosis Clinic within 6 months, then the data from the Osteoporosis Clinic may be used and subject does not need to complete a scan specifically for the research study.

During the study, subjects will be regularly monitored for adverse effects of exercise during clinic visits and telephone contacts. In addition, participants can report adverse events (AdEs) by telephone at any time. The PI will contact participants by telephone if any reported AdE suggests clinical deterioration warranting immediate medical attention. Subjects in both arms will be instructed to notify study staff if they experience any change in their clinical condition, any change in medications, or have urgent care visits, emergency room visits, or hospitalizations. During the study, if a subject experiences a medical problem that prevents walking and exercise, he will be temporarily suspended from the study and will resume when at baseline clinical status. Any AdEs that are immediately life-threatening, cause permanent or lasting harm, or require a hospitalization will receive a serious classification. All serious adverse events (SAE) and unanticipated problems will be reported to the respective IRB at continuing review but reported to the study DSMB immediately. If an event is possibly, probably or definitely related to the intervention, it will be classified as intervention-related. Based upon our prior experience, the most common SAE will be hospitalization for a COPD exacerbation. The most common AdE will be musculoskeletal injuries.

We have convened an independent, external Data and Safety Monitoring Board (DSMB). They will monitor the rates of AdEs and SAEs and unanticipated problems between the 2 arms of the study. The DSMB is composed of [name] an expert in pulmonary rehabilitation and COPD clinical trials at Boston Medical Center, [name] an expert in telemedicine methods in COPD at Southern California Kaiser Permanente, and [name], PhD, NP an expert in patient-centered coaching and behavioral change methodologies and

interventions in persons with COPD at Touro University of California. They will meet every 6 months, and as needed, by telephone conference.

### **(3) Potential Benefit of the Proposed Research to the Subject and Others.**

There is potentially great benefit to the large number of persons with COPD if the proposed work leads to the adoption of an Internet-mediated walking program to promote physical activity in clinical practice. Such walking programs would be accessible to all who needed it and would improve short- and long-term outcomes. Since risks of the study are minimal, and the societal benefits are potentially large, the risk-benefit ratio is strongly on the side of benefit. There are no direct benefits to the subject.

Although not all participants may experience benefits, some of the potential benefits of participating in the study include more effective management of COPD symptoms, increased exercise capacity, and better quality of life.

Potential benefits to others include contributing to the development of an accessible, individualized, and sustainable program that incorporates strategies for behavioral change for managing COPD symptoms to encourage physical activity in those with COPD.

The risks to the subjects are reasonable in relation to the anticipated benefits to subjects and others because each participant is required to obtain medical clearance which indicates they are healthy enough to participate in a walking program. Additionally, walking carries minimal risk, and physical activity is part of usual care for managing COPD symptoms.

### **(4) Importance of the Knowledge to Be Gained.**

Although it is well known that greater physical activity is beneficial, it is unclear how to increase physical activity in persons with chronic disease such as COPD who already experience functional disability from their disease. Novel strategies are needed to promote physical activity and exercise in persons with COPD. The proposed pedometer-based, Internet-mediated walking program is unique because of its automation, ability to accurately monitor walking performed, individualized step-count goals, and educational content and motivational messages. We propose to rigorously assess the efficacy of the Walking and Education to Breathe (WEB) exercise intervention in a randomized controlled study and to examine its effect on short- and long-term outcomes in COPD. These are the next steps needed to rigorously examine if WEB works.

If successful in increasing 6MWT distance and improving short- and long-term outcomes, such a program would have a direct and positive impact on the way we currently care for persons with COPD. Once implemented, such a program would be available to all persons with COPD who needed it, would individualize exercise training, and could promote walking indefinitely. Based on published estimates that 24 million people in the US have COPD and our preliminary data that 33 to 64% of COPD patients are Internet users, our proposed intervention could help over *8 million* persons. The number of people who uses the Internet will continue to increase, making such an approach to promote physical activity ideal to reach a large number of patients.

Our proposal addresses the exciting and important next steps of developing novel interventions to increase physical activity and assessing the impact of those interventions on COPD outcomes. Our highly clinically relevant intervention has the potential to (1) bring an exercise program to the vast majority of persons with COPD who cannot go to a hospital-based pulmonary rehabilitation program, (2) improve the effectiveness of current pulmonary rehabilitation programs, and (3) become an integral part of COPD self-management programs. Ultimately, the intervention could decrease risk of hospitalizations, acute exacerbations, and COPD-related morbidity and mortality.

I. **Animal Subjects**: This study does not use animal subjects.

(5) **Resources**

(a) **Research Space:**

All in-person study visits will be conducted in VA space either at VA Boston or VA Birmingham. At VABoston, in-clinic study visits will be conducted at the West Roxbury, Jamaica Plain, or Brockton campus.

All blood samples will be shipped to MAVERIC where they will be processed and stored.

The website is maintained by staff at the University of Michigan. Step-count data are located on the University of Michigan server.

(b) **Other Research Resources:**

There is a separate 300 ft exam room used for research activities such as subject enrollment, questionnaire administration, and spirometry using an Eaglet portable spirometer (nSpire Health, Inc.). Pulmonary function tests can also be performed in the dedicated research pulmonary function laboratory (150 ft) with a computerized Collins CPL pulmonary function system and Collins portable water seal spirometer. The 6-minute walk test is performed using a well-marked course in a straight corridor.

[name] office is part of an epidemiological research group that occupies 1500 ft of dedicated office space at the West Roxbury campus. [name] office and research laboratory occupy 800 ft of office space and has office network of high speed PC's linked via a network. Software capabilities include PC-SAS, STATA, and standard data management software (Microsoft ACCESS, EXCEL, Word). There is a network of 8 high-speed PC's with large capacity data storage capacity with back up and linkage among password protected PC's provided by the hospital network.

The VA Boston Healthcare System is an academic affiliate of Harvard Medical School and Boston University School of Medicine. The VA Boston Healthcare System, West Roxbury Campus, is located 8 miles from the Harvard Medical area, which includes the Francis A. Countway Library of Medicine, Harvard Medical School, and the Harvard School of Public Health. Through the Countway Library we have computerized access to one of the largest medical libraries in the United States that contains over ½ million books and receives over 4,000 journal titles, and access to one of the most comprehensive search services in the country.

## **Addendum to Protocol: Brain MRI Scan Substudy**

**Rationale:** COPD is the nation's third leading cause of death and affects up to 11% of all VA healthcare patients. Patients with COPD experience significant dyspnea despite optimization of medical therapy. In addition, over half of patients with COPD experience chronic pain—largely musculoskeletal pain. Clinically, in patients who suffer from both chronic pain and dyspnea, it is difficult to distinguish a patient's perception of one symptom, modulated or amplified by the other, using self-report and questionnaires. Yet, it is critically important to differentiate them to make accurate diagnostic and treatment decisions. Patients who experience and report pain, heightened by worsening dyspnea, may be overtreated with narcotics which can lead to respiratory suppression or opioid dependence. Similarly, a patient's report of dyspnea, amplified by worsening chronic pain, may lead to unnecessary testing for etiologies of dyspnea and undertreatment of pain. To optimize clinical management, novel objective diagnostic tools are needed to complement patient self-report and accurately distinguish symptoms in patients who have combined chronic musculoskeletal pain and dyspnea.

It is also important to understand chronic musculoskeletal pain and dyspnea because they are common barriers to engaging in PA and exercise. The clinical course of COPD is characterized by a downward spiral of dyspnea, physical inactivity, and deconditioning. Chronic musculoskeletal pain similarly leads to a negative cycle of physical inactivity and deconditioning, ultimately resulting in significant physical limitation. Although chronic musculoskeletal pain and dyspnea can be barriers, PA and exercise are powerful, but underused non-pharmacological therapies for management of these symptoms in COPD. We developed Every Step Counts (ESC), a technology-mediated intervention based on the Theory of Self-Regulation, to promote PA in COPD. ESC couples a pedometer with a dynamic website that provides individualized step-count goals, iterative feedback, education on disease self-management, motivation, and an online community of social support. In two randomized studies in Veterans with COPD, we demonstrated ESC's safety, feasibility, and efficacy to increase PA and improve health-related quality of life over 3-4 months. In preliminary studies using questionnaires, we showed that ESC can improve dyspnea. In a separate study, the same PA platform has also been shown to relieve chronic back pain in Veterans. An important next step is to understand the effects of PA interventions, like ESC, in the many COPD patients with combined chronic musculoskeletal pain and dyspnea to ultimately improve PA interventions and personalize treatment of symptoms.

**Background:** Unique brain activity networks and specific structural changes in the brain are traditionally associated with chronic pain stimuli. It has been shown that resting state functional connectivity, between the anterior insular cortex and brainstem periaqueductal gray, determines pain perception in healthy humans. Resting state functional connectivity magnetic resonance imaging (fcMRI) is used in brain mapping to evaluate interactions and communications between brain regions that occur in a resting state, before a sensory event or when an explicit task is not being performed. The resting pattern and strength of functional connectivity specifically within the "default mode" network (DMN) (posterior cingulate, inferior parietal lobes, and medial frontal gyrus) have been examined in several studies of clinical disease states, as this network is reliably detected and well-characterized. The DMN is an anatomically defined brain system that is one of the most studied networks present during resting state and is one of the most easily visualized networks. It is a critical network involved in many functions with high interconnectivity with other networks and could be a sensitive network to examine in response to symptom changes. These resting communications are altered in older adults with chronic musculoskeletal pain who show greater functional connectivity between the posterior cingulate and left insula, superior temporal

gyrus, and cerebellum. Chronic musculoskeletal pain in COPD has not been studied with neuroimaging.

Currently, the central mechanisms of chronic musculoskeletal pain and dyspnea, and how they change in response to PA promotion, in COPD are largely unknown. Unique brain activity networks and specific structural changes in the brain are traditionally associated with chronic pain stimuli. It has also been shown that resting state functional connectivity determines pain perception in healthy humans. Resting state fMRI evaluates interactions between brain regions before a sensory event or when an explicit task is not being performed. These resting regional communications are altered in older adults with chronic musculoskeletal pain. Functional connectivity among regions specifically within the “default mode” network (DMN) (posterior cingulate, inferior parietal lobes, and medial frontal gyrus) have been examined in clinical disease states, as this network is reliably detected and well-characterized. Resting state functional connectivity may be a novel biomarker, complementing patient self-report, that tracks the unique contributions of chronic pain and dyspnea to a patient’s symptom complex. No studies to date have examined the relationships between subjective measures of chronic pain and dyspnea and objective measures of functional connectivity, or changes in these symptoms and functional connectivity in response to PA promotion in persons with COPD.

**Objective:** Assess the feasibility of conducting brain fMRI in persons with COPD and begin to understand the central mechanisms of chronic musculoskeletal pain and dyspnea, and how they associate with physical activity. This will be done by the following:

- (1) Recruit from persons who are currently or have previously participated in the WEB study to assess if they would participate in an additional in-person visit to complete an fMRI scan assessment.
- (2) Recruit up to 20 of those persons willing to receive an MRI scan at VA Boston to assess feasibility of obtaining fMRI and gather preliminary data on the relationships between patterns of functional connectivity and shortness of breath, chronic musculoskeletal pain, and physical activity in COPD to design a future study.

### **Work Proposed:**

**Recruitment:** An approved HIPAA waiver will allow contact of those who have completed the main study. We will contact these participants by letter and then by telephone if there is no response after 2 weeks. Those who are in follow-up in the main study will be approached in person, and eligible and interested participants will sign an ICF and HIPAA specific to the substudy. For all participants in the substudy, the fMRI can be done at the same visit as scheduled for the main study or during a separate visit depending on participant preference.

**Proposed MRI assessment:** Among those persons willing to participate in an MRI scan assessment, we will ask up to 20 of these subjects to undergo an fMRI scan at VA Boston. Participants will complete a dedicated VA consent form and HIPAA authorization for the MRI scan at the time of the MRI scan, as well as an MRI scan clearance form. Scans will be performed in the Neuroimaging for Veterans Research Center (NeRVe) of the VA Boston Healthcare System, and a clinical MRI technician will be present for all scans.

*For the proposed substudy, additional exclusion criteria are:*

- Claustrophobia
- History of seizures
- Current diagnosis of bipolar disorder, schizophrenia, or psychotic disorder
- Cognitive disorder such as dementia

- Known metal in body including shrapnel, surgical medical clips, implants, pacemakers, or metal-based tattoos
- Known or new brain lesions (including but not limited to brain cancer, metastatic cancer, subdural hematoma)

Each scan will start with 5 minutes of familiarization with the equipment and will be completed at one visit that lasts approximately 90 minutes. Physiologic monitoring will be synchronized with image acquisition. Chest expansion, oxygen saturation, and end-tidal CO2 will be assessed. We may apply some sensors on the hand and chest, as well as install a respiration belt around the torso and a gas mask that will record breathing rate. Neuroimaging data will be acquired on a 3-Tesla Siemens (Erlangen, Germany) TIM Trio scanner, using a 32-channel brain array. Two multiecho MPRAGE (Magnetization Prepared Rapid Gradient Echo) T1-weighted anatomical scans (1 mm isotropic) will be acquired for surface reconstruction, functional connectivity seed placement, and inter-participant registration. Resting state functional connectivity data will be acquired in two runs using high temporal and spatial resolution sequences recently developed for the Human Connectome Project Lifespan study.

The scans performed in this study are for specific research purposes and are not meant to find any medical abnormalities. The results from the research scan will not be routinely shared with the participant's clinical provider, except upon the participant's request. However, if the investigators or MRI technician notice any potential incidental finding, the scan will be reviewed by a clinical radiologist who will determine whether a clinical evaluation is warranted. If there is a finding that warrants a clinical follow-up, study personnel will discuss this with the participant. If any abnormality on the MRI is noted by the research staff, the participant will be notified to follow up with his usual provider.

Eligible subjects will also complete an MMRC Dyspnea Scale assessment and the Brief Pain Inventory (short form) before having the brain MRI.

Persons will receive \$25 compensation in cash for their participation in the fcMRI assessment.

In addition to the information collected from the fcMRI, we may also use other information obtained as part of the subject's participation in the main study including name, address, date of birth, and information such as SSN, pulmonary function tests, laboratory test results, X-ray images/readings, exercise tests, hospitalization records from other institutions, emergency contact information, pulmonary rehabilitation evaluations, medical history, allergies, imaging studies and reports, procedure reports, drug, alcohol, or STD treatment, genetic test results, or mental health treatment.

### **Risks to Subjects:**

*Potential Risks:* Neuroimaging with MRI Scanning: Minimal risks are associated with MRI scanning. Extended periods of time in the MRI scanner can become uncomfortable. Lying down in the MRI scanner may cause back discomfort or anxiety, particularly if the subject tends to be claustrophobic. There is a risk of falling getting on and off the scanner table. There is no risk of ionizing radiation exposure with MRI.

During the MRI procedure, participants will hear many different sounds. These sounds are sharp and repetitive and can cause anxiety in some subjects. While they may be annoying, these sounds are not harmful to one's hearing.

Interested participants will provide written informed consent obtained by trained and experienced study staff. VA Boston research staff will explain the nature, scope, and possible consequences of the substudy in a way that is understandable to participants and answer all their questions. Participants can discuss the substudy with their usual healthcare providers. Subjects can participate in the primary RCT without obligation to participate in the brain MRI scan substudy.

*Protection Against Risks:* We will use all reasonable means to promote comfort including but-not limited to use of pillows and padding. Some people experience a "closed-in" feeling due to the relatively restricted space within the MRI machine. If a participant should experience such feelings, he can let the researchers know by squeezing the squeeze ball. He can do this at any time to stop the scan. We will minimize sharp sounds through the use of earplugs.

All safety precautions will be reviewed with the subject immediately prior to having the MRI. If there is any doubt as to whether the subject has metal in his body, he will be requested to have an X-ray to determine this. If the X-ray shows that there is metal in the participants, he will not be able to take part in the MRI study. If there is more than one part of the body in which metal is questionable, the participant will not be able to have an X-ray and will not be able to participate in the MRI study.

Study staff will provide pillows and close verbal communication to minimize anxiety and discomfort. The criteria for discontinuing a subject's participation in the neuroimaging protocol include the participant's request, any potential for harm, and any life-threatening or potentially disabling unintended event, including syncope, an injurious fall, new or worsened symptoms of musculoskeletal pain, shortness of breath, or chest pain, hemodynamic instability, mental status changes, dysrhythmia, angina, myocardial infarction, or anaphylaxis. These adverse events will be recorded and included in the database. Any subject who develops adverse events during the conduct of study protocols will be given immediate medical care and will be referred to his primary care physician for ongoing care.

Available 24/7 for emergencies, [name], the PI, will contact participants if any telephone reported adverse event suggests clinical deterioration warranting immediate medical attention. Participant confidentiality and data security will be maintained at all times. Each participant will be given a unique study ID that will be used for all research purposes. Neuroimaging data will be stored behind the VA firewall at VA Boston. These data are backed up every night. The document linking the participant name to the study ID will be kept in a locked file separate from data collection files. Only the Principal Investigator or designee will have access to this file.

**Analytic Approach:** For neuroimaging, all analyses will be performed with complementary advanced imaging procedures for brain network mapping, including seed-based and independent component analysis procedures, to assure the robustness of the findings. We will correlate neuroimaging data with clinical data obtained at baseline in the main study, including demographics, dyspnea, chronic pain assessments, and daily step count as the measure of PA. We will perform secondary analyses to examine the potential influence of PA and clinical characteristics that may contribute to the findings. We will be somewhat exploratory in our approach in this pilot project, while also being mindful of statistical considerations. Our main image analyses will use robust and careful seed based DMN mapping procedures. Analyses will account for known contributors to the fcMRI signal including motion, respiration and cardiac signals. Neuroimaging data will be processed using a combination of FreeSurfer. AFNI. and FSL. based primarily on the FSL processing stream. Surface models will be reconstructed from anatomical images using FreeSurfer. Resting state fcMRI scans for each subject will be

processed using a standard stream (motion correction, time shifting, concatenation of scans, motion regressed from time series, regression of the global mean and the average time courses from the white matter and the ventricles, band pass filtering between 0.01 and 0.1 Hz). Time points, runs, and sessions with excessive motion will be excluded (0.5 mm/TR; 20 TRs/run; 30 TRs/session). Data will be sampled to and smoothed on the surface, and each brain will be warped to a surface-based template (fsaverage). Seed regions will be derived from surface-based parcellations of the cortex providing more robust anatomical representation for each participant. The vertex-wise partial correlation to the seed will allow further group-level analyses. We will focus on the DMN, but explore other networks including pain networks. We will also explore resting state functional connectivity associated with the anticipatory symptom scenarios.

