
#### (4) **Work Proposed**

- (a) Provide a timetable describing the sequence of the proposed research.

Staff training, IRB approval and finalization of website specifications and beta testing will occur during the first 6 months of Year 1.

Recruitment and randomization would begin the second half of Year 1: Recruitment will be conducted over 30 months to achieve the goal to randomize up to 185 subjects. We anticipate enrolling 3-4 subjects per site each month through the third quarter of study year 3 (Figures 2 and 3). Between both sites, we expect to screen and enroll a total of 320 participants in order to randomize a total of 185 participants for the whole study.

Subjects will have completed their participation in the study after approximately 13 months from the first in-clinic baseline visit.

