**Statistical analysis:**

Group average correlation maps will assess cross-sectional associations between functional connectivity patterns and daily step count, dyspnea, and chronic musculoskeletal pain. We will also explore differences in functional connectivity in those with predominantly pain versus those with predominantly dyspnea.

**Sample size/Power calculation:** This is an exploratory proposal in a convenience sample of up to 20 Veterans with COPD. Findings from this study will inform the design and sample size of a future Merit Award application.

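### The MRI substudy's stated analysis uses main-study baseline symptoms, possibly 13 months old or more, and never names the dyspnea and pain scores taken at the scan

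*Combined protocol and SAP*

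**What the plan says.** All of this is in the Addendum to Protocol: Brain MRI Scan Substudy, except the trial timetable.

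- **Source of the clinical data (Analytic Approach).** "We will correlate neuroimaging data with clinical data obtained at baseline in the main study". The sentence goes on to list the variables: "including demographics, dyspnea, chronic pain assessments, and daily step count as the measure of PA". No other sentence in the addendum says which measurement occasion feeds the analysis.
- **Who is scanned (Objective; Recruitment).** "Recruit from persons who are currently or have previously participated in the WEB study". For people who have finished: "An approved HIPAA waiver will allow contact of those who have completed the main study". Those still in follow-up are approached in person. On timing, "the fMRI can be done at the same visit as scheduled for the main study or during a separate visit depending on participant preference".
- **What is measured at the scan (Proposed MRI assessment).** "Eligible subjects will also complete an MMRC Dyspnea Scale assessment and the Brief Pain Inventory (short form) before having the brain MRI". No step count is listed.
- **Type of association (Statistical analysis).** "Group average correlation maps will assess cross-sectional associations between functional connectivity patterns and daily step count, dyspnea, and chronic musculoskeletal pain". The same section adds an exploratory comparison of participants in whom pain predominates with those in whom dyspnea predominates. It does not say when that is judged.
- **Length of the trial (main protocol, section 4, timetable).** "Subjects will have completed their participation in the study after approximately 13 months from the first in-clinic baseline visit".

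**The concern.** The scan records brain connectivity on one day. Under the stated analysis it is paired with symptoms and activity recorded before randomization, on a date that differs from person to person and has no upper limit on its distance from the scan.

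The sponsor expects these same variables to move in the interval. The main protocol (Specific Objectives) hypothesizes that WEB improves dyspnea and daily step count. The addendum's rationale says that the related ESC program can improve dyspnea and that the same platform has relieved chronic back pain. Any such change would come between baseline and scan and could differ by arm. Neither analysis section mentions treatment arm or elapsed time.

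More suitable dyspnea and pain scores will exist, because they are collected immediately before the scan. If the analysis leaves them unnamed, two sets of scores are available and the choice could be made after the results are seen. The correlations are meant to inform the design and sample size of a later application, so weakened estimates would carry forward.

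**Working it through.** The substudy states no effect size, alpha or power, so there is no planned figure to reproduce. The check sets the sections side by side and then illustrates the possible size.

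**1. Age of the baseline data at the scan**

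- *Participants in follow-up:* the scan may coincide with a trial visit or not. At the visits in months 3, 6 and 12 the gap is about 3, 6 or 12 months.
- *Completers:* the timetable gives about 13 months from the baseline visit. Under Minimizing Attrition and Handling Missing Data, month 12 has a window of ±1 month, so the final visit falls between 12 − 1 = 11 and 12 + 1 = 13 months. The scan comes later, and no maximum is set.

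Baseline values of 13 months or more are therefore possible, though not universal.

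**2. Consistency of the sections**

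| Section of the addendum | Measurement occasion implied |
|---|---|
| Analytic Approach | Main-study baseline |
| Proposed MRI assessment | Scan day, for MMRC and Brief Pain Inventory |
| Statistical analysis | Same time as the scan (cross-sectional); source not named |
| Statistical analysis, pain versus dyspnea groups | Not stated |

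Both recruitment routes reach people already past baseline. Correlating their scans with baseline values is not cross-sectional.

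**3. Illustration of the attenuation (assumptions, not document figures)**

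Assume one correlation, n = 20, two-sided alpha 0.05 and a true scan-day correlation of 0.60. Let s be the correlation between the baseline and scan-day scores. If connectivity relates to the baseline score only through the scan-day score, then

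expected r = 0.60 × s

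Power ≈ Φ(atanh(r) × √(n − 3) − 1.96), with √17 = 4.123; the opposite tail is negligible.

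| s | Expected r | atanh(r) × 4.123 | Power |
|---|---|---|---|
| 1 (scan-day score) | 0.60 | 0.693 × 4.123 = 2.858 | Φ(0.898) ≈ 82% |
| 0.9 | 0.54 | 0.604 × 4.123 = 2.491 | Φ(0.531) ≈ 70% |
| 0.7 | 0.42 | 0.448 × 4.123 = 1.846 | Φ(−0.114) ≈ 46% |
| 0.5 | 0.30 | 0.310 × 4.123 = 1.276 | Φ(−0.684) ≈ 25% |

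The value 0.60 lies close to the correlation detectable with 80% power at n = 20: tanh((1.960 + 0.842) / 4.123) = 0.59. The first row therefore looks adequately powered because of the value chosen. The column to read is the expected r.

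**The case against.** The strongest reply is that nothing excludes the scan-day scores. They are collected just before the scan, the Statistical analysis section describes cross-sectional associations without giving a source, and the two can be read together as intending scan-day data. It follows that a reader should not infer a decision to discard those scores; the documents leave their use unspecified. But the reply needs the reader to override the one sentence that does name a source, so the contradiction remains.

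Four other strong readings are tempting and not supported:

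- *That this is the substudy's only comparison.* The plan also compares pain-predominant with dyspnea-predominant participants, adds secondary analyses, and has feasibility as an aim. Symptom timing does not touch feasibility.
- *That about half of those scanned will have had WEB.* The 1:1 ratio belongs to the trial. The substudy is a convenience sample and its split by arm is unknown.
- *That the power figures measure the loss.* They depend on an assumed effect and assumed stability. The planned analysis is a set of vertex-wise seed maps, not one correlation test.
- *That rewording alone cures everything.* It does so for dyspnea and pain, not for step count.

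It is also fair to say that chronic pain may be fairly stable, so an earlier value is not worthless. That argues for the upper end of the illustrated range.

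**Conclusion.** The point holds as a conflict within the addendum. Its only sourced sentence uses main-study baseline data, while its recruitment, its scan-day assessments and its description of the associations point to data from the time of the scan. Followed as written, the analysis would pair scans with pre-randomization values whose age varies, with the intervention in between for some participants.

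The probable consequence is correlations biased toward zero, by a factor equal to the stability of each score under the simple model above. That stability is not in the documents; over an assumed 0.9 to 0.5, a true 0.60 becomes 0.54 to 0.30. Differential change by arm could distort the correlations further, in a direction that cannot be stated in advance.

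The reach is limited to an exploratory pilot of up to 20 people and the later study it informs. The trial's main results are not affected. The change is worth making because it is cheap and fixes the choice of scores before analysis.

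**What to change.** Amend Analytic Approach and Statistical analysis in the addendum as follows.

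1. Name the scan-day MMRC and Brief Pain Inventory as the main symptom variables, both for the correlations and for defining the pain-predominant and dyspnea-predominant groups.
2. For physical activity, use the main-study step-count window nearest the scan, defined in the same way in both arms, and report the interval between that window and the scan.
3. Report treatment arm and time since baseline for every scanned participant.
4. Keep the main-study baseline values as a secondary analysis, labelled as such.

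**Cost.** For dyspnea and pain, wording only, since the scores are already to be collected. For physical activity the remedy is partial. The last collection for completers is around month 12, which may be well before the scan; the addendum should say so as a limitation. Removing that gap would need a new pedometer collection near the scan, which is extra work and not just rewording.
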